11. RECRUITMENT AND PROCEDURES PREPARATORY TO RESEARCH

Enrollment. Surgeons, anesthesiologists or their counterparts (e.g., CRNAs, PAs) at each enrolling center will identify potential study subjects at preoperative patient visits prior to a planned amputation. Surgeons will be seeing patients as part of regular medical care, and therefore this protocol will adhere to Health Insurance Portability and Accountability Act (HIPAA) regulations.

Alternatively, the investigators may need to contact potential subjects prior to their pre-surgery visit and therefore request a waiver of consent for recruitment purposes. We would scan the upcoming ambulatory surgery schedule (which we have access to being anesthesiologists—we use this schedule daily for medical purposes), identify patients having the types of surgical procedures specified for this study, look in their electronic records to determine eligibility, and if eligible either call the potential subjects ourselves or provide the name and contact information to a research coordinator to contact the potential subjects.

1. These procedures are minimal risk to the potential subjects as we are anesthesiologists who will be viewing these records even without study participation in preparation for surgery and postoperative analgesia planning. There is no information that an anesthesiologist would not view regardless of the existence of the study.
2. A waiver of consent would not adversely affect the rights and welfare of the potential subjects as we are anesthesiologists who will be viewing these records even without study participation in preparation for surgery and postoperative analgesia planning. There is no information that an anesthesiologist would not view regardless of the existence of the study.
3. This clinical trial could not be practicably carried out without the waiver because many relatively healthy ambulatory patients are not seen in preop clinic; or, they are seen just 1-2 days prior to their date of surgery. We need to bring subjects into clinic within the 7 days prior to their surgery to have their leads inserted. We do not have enough time to do this the morning of surgery.
4. After subjects are contacted, if they would like to participate they will receive written, informed consent using an IRB-approved informed consent form.

These procedures would also include access to PHI, so we request a partial waiver of HIPAA authorization to be granted:

1. Identifiers will include the potential subject's date of surgery, surgeon, name, phone number, and email address (to send ICF if patient is interested in participation). This information will be recorded in hard-copy format and destroyed using a paper shredder (or in the locked UCSD PHI disposal stations) following contact with the patient. If the patient does not participate, then there will be no record of PHI whatsoever. If the patient does participate, then PHI will be protected as described in #16 below.
2. This clinical trial could not be practicably carried out without the waiver because many relatively healthy ambulatory patients are not seen in preop clinic; or, they are seen just 1-2 days prior to their date of surgery. We need to bring subjects into clinic within the 7 days prior to their surgery to have their leads inserted. We do not have enough time to do this the morning of surgery.
3. The privacy risk to individuals whose PHI will be used is minimal since, as anesthesiologists at UCSD caring for ambulatory surgery patients, we use the surgery schedule daily in the normal course of our work caring for patients; and, we will not record any PHI other than date of surgery, surgeon, name, contact phone numbers, and email address—and, these will be destroyed following use. The anticipated benefit to subjects is a chance of improving their postoperative pain control if they are randomized to active stimulation.

4. PHI that will be used includes date of surgery, surgeon, name, contact phone numbers, email address, basic anthropomorphic data such as height and weight, past medical and surgical history, and the surgical schedule itself. Only coinvestigators will access this PHI, and the only people they might share it with are research coordinators actively participating in this research who understand PHI procedures and to appropriately destroy the hard copy of date/surgeon/name/contact numbers/email address after use.

Patients meeting inclusion and exclusion criteria will be presented with the study, and prospective study subjects desiring additional information will be required to give permission for a research coordinator to contact them to adhere to HIPAA requirements. The study protocol will be reviewed with interested prospective subjects in detail; and, for subjects desiring participation, written, informed consent will be obtained prior to any measurements, data collection, and/or interventions. The method of documenting consent will be using written informed consent forms approved by the local Institutional Review Board.

12. INFORMED CONSENT

Once a prospective subject contacts (or gives permission to be contacted by) an investigator or research coordinator by telephone or email, they will be provided information on the study purpose and protocol, as well as have any questions answered. Candidates who meet inclusion and exclusion criteria and desire study enrollment will be scheduled to arrive the day of surgery earlier than normal to allow for written informed consent and baseline instruments to be applied. Written informed consent will be attained prior to any measurements or procedures prior to surgery. Each site director is responsible for ensuring that written, informed consent is obtained from every subject at their respective enrolling center. Clinical research coordinators—also one for each enrolling site—will be specifically trained by the site directors to provide informed consent followed by documentation of informed consent using an Institutional Review Board-approved informed consent form. When subjects present for surgery, research coordinators will provide and attain written informed consent. This will occur in private patient care areas, so that subjects may feel comfortable asking questions of the research coordinator. If a subject desires—or if there is a question that a research coordinator cannot answer—the site director will be called in by the research coordinator to discuss the study directly with the subject.

We do not foresee any issues relevant to the mental capacity of the potential human subjects. Written, informed consent will be attained prior to any study procedures or measurements; and, subjects will not receive procedure-related sedation until following the written, informed consent process is completed. Subjects will be provided privacy and time for decision making both in the study description/explanation telephone call to the site director or research coordinator, as described above; and also the morning of the initial treatment using a private patient care area to again review the study, informed consent form, and answer any remaining questions. As noted previously, subjects may speak with the site director by telephone from initial contact through the morning of treatment; and, will have access during and following the treatment(s) with cellular phone and pager numbers provided upon discharge.

This study protocol has follow-up data-collection telephone calls a maximum of 1 year following the initial study treatment, so repeated informed consent following the initial consent is unnecessary, as opposed to multi-year, longer-term clinical trials. Surrogate consent will not be accepted; therefore, if

human subjects cannot provide consent on their own, they will not be offered study enrollment. Consent by an individual's Legally Authorized Representative is unacceptable for study enrollment.

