Specific Aim 1 (UG3): To determine the **feasibility** and **optimize** the protocol of the Implementation Phase (UH3) multicenter clinical trial that will compare percutaneous PNS with usual and customary opioid-based analgesia following moderate-to-severely painful ambulatory surgery.

Specific Aim 2 (UG3): To **estimate** the **treatment effect** of percutaneous PNS on pain and opioid consumption following moderate-to-severely painful ambulatory surgery compared with usual and customary opioid-based analgesia. This will allow determination of the required **sample size** of the definitive multicenter clinical trial of the Implementation Phase (UH3).

Therefore, the protocol for the UG3 Planning Phase feasibility study and the UH3 Implementation Phase pragmatic trial will be identical, with the exception of any improvements determined by the UG3 study.

Enrollment. Surgeons at each enrolling center will identify potential study subjects at preoperative patient visits. Surgeons will be seeing patients as part of regular medical care, and therefore this protocol will adhere to Health Insurance Portability and Accountability Act (HIPAA) regulations. Patients meeting inclusion and exclusion criteria will be presented with the study, and prospective study subjects desiring additional information will be required to give permission for a research coordinator to contact them to adhere to HIPAA requirements. Research coordinators will review the study protocol in detail with interested prospective subjects; and, for subjects desiring participation, written, informed consent will be obtained prior to any measurements, data collection, and/or

[figure not shown]
interventions. The method of documenting consent will be using written informed consent forms approved by the local Institutional Review Board.

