Data collection. Much of the surgical data from the day of surgery will be extracted from electronic health records to leverage data collection that occurs in health care delivery rather than requiring independent research data collection. Subject demographic, surgical and percutaneous PNS administration data will be uploaded from each enrolling center via the Internet to a secure,¹⁴⁴ password-protected, encrypted central server (RedCap, Department of Outcomes Research, Cleveland Clinic, Cleveland, Ohio).¹⁴⁵ All data collection following the day of enrollment (postoperative day 0)—regardless of enrolling center—will be collected by telephone from the University of California San Diego. Staff masked to treatment group assignment will perform all assessments.

UG3 Milestones. The 2-year UG3 feasibility period has explicit milestones (**Table 3**, following page) that are feasible, quantifiable, and scientifically justified to allow an assessment of progress. **Each of the items listed in Table 3 and the following outline is considered a milestone and must be completed in order to proceed to the 4-year UH3 definitive, pragmatic clinical trial.**

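### Section 12 schedules written consent for the day of surgery, but Section 11 puts lead insertion at a clinic visit before that day for at least some subjects

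*Combined protocol and SAP*

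**What the plan says.** Section 12 (Informed Consent) fixes the time of written consent twice. Candidates who qualify and wish to enroll "will be scheduled to arrive the day of surgery earlier than normal to allow for written informed consent and baseline instruments to be applied". Later in the same section: "When subjects present for surgery, research coordinators will provide and attain written informed consent".

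Section 9 (Research Design and Methods, *Data collection*) treats enrollment as happening on that same day: "All data collection following the day of enrollment (postoperative day 0".

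Section 11 (Recruitment and Procedures Preparatory to Research) puts lead insertion elsewhere. In the rationale for the waiver of consent for recruitment, and again in the rationale for the partial HIPAA waiver, it says: "We need to bring subjects into clinic within the 7 days prior to their surgery to have their leads inserted". Each time it adds: "We do not have enough time to do this the morning of surgery".

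The ordering rule appears in three sections. Section 9 (*Enrollment*): "written, informed consent will be obtained prior to any measurements, data collection, and/or" interventions. Section 11: "written, informed consent will be obtained prior to any measurements, data collection, and/or interventions". Section 12: "Written informed consent will be attained prior to any measurements or procedures prior to surgery".

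**The concern.** Lead insertion is a study procedure: a needle and lead are placed near a nerve and test stimulation is given. If it takes place at a clinic visit before the day of surgery, while written consent waits for arrival on that day, the subject has the procedure first and signs afterwards. A coordinator cannot follow both the Section 12 schedule and the consent-first rule for such a subject.

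What is at stake is subject protection and regulatory standing. Section 14 lists discomfort or pain on insertion or during stimulation at 10% and lead fracture at 7.5%, among other risks that a subject should accept in writing before the lead goes in. The early visit is also part of the argument for why the trial needs the two waivers. An ethics board is therefore given one timeline in the waiver request and another in the consent section of the same protocol.

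**Working it through.** The point concerns the order of events, so the check is a comparison of text. The only arithmetic is the length of the gap.

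**1. The stated timings side by side**

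| Event | When | Where stated |
|---|---|---|
| Written consent | Day of surgery, on early arrival | Section 12, stated twice |
| Enrollment | Postoperative day 0 | Section 9, *Data collection* |
| Lead insertion (alternative route) | Clinic visit in the 7 days before surgery; morning of surgery ruled out | Section 11, stated twice |
| Lead insertion (general) | Before the nerve block; no calendar day | Section 9, *Lead insertion* |
| Consent relative to procedures | Consent first | Sections 9, 11 and 12 |

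**2. Can the first, third and fifth rows all hold for one subject?** Let surgery be day 0. Section 12 puts consent on day 0. Section 11 puts insertion no earlier than day −7 and not on the morning of day 0. The ordering rule needs consent before insertion. Consent on arrival for surgery cannot precede an insertion done at a visit before that day, so the three statements are incompatible for any subject with an early insertion.

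**3. Length of the gap.** The maximum is 0 − (−7) = 7 days, taken directly from Section 11. A minimum of 1 day follows only by inference: if the morning of surgery is excluded, the latest visit is the day before. The documents do not state a minimum.

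**4. Which text is wrong?** Section 9 runs from consent, to baseline measurements, to lead insertion, and then to a separate step labeled for the day of surgery. Item 4 of the waiver rationale in Section 11 has written consent following contact with the subject. Both agree with the ordering rule. The day-of-surgery schedule in Section 12 and the enrollment phrase in Section 9 do not fit when insertion is early.

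**5. Does it reach the statistics?** Under *Treatment group assignment* in Section 9, allocation occurs only after the lead is confirmed in place and surgery has begun. Consent timing is therefore common to both arms. The primary models in the Statistical Plan are a mixed model for daily pain with treatment and time, and a regression of log cumulative opioid dose on treatment. Neither has a term that depends on the date of consent. The sample size inputs do not involve it either.

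**The case against.** The strongest reply is that nobody plans to treat without consent. The ordering rule is stated repeatedly, once directly after the quoted scheduling sentence. Section 12 also withholds procedure-related sedation until consent is complete, and it provides for a review of the form on the morning of the initial treatment, which could be read as the insertion visit. Section 11 collects email addresses so that the form can be sent ahead. On this view one scheduling sentence was simply not updated. That is right about intent, and a reader who inferred a deliberate plan to insert leads before consent would be going beyond the documents. It does not remove the conflict. The general rule does not tell a coordinator which day to book, whereas Section 12 does so twice and names surgery both times. The review that morning is a second review, and sending a form is not signing it.

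The second reply concerns reach, and it stands. The 7-day text sits in a waiver rationale under a route introduced as an alternative, and the HIPAA item speaks for anesthesiologists at one of the seven centers. A reader might infer that every subject, or every center, is affected. The documents do not support that, because Section 9 gives no calendar day for insertion and no number of early visits is stated.

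A third point limits what can be said about practice. The consent pages are not in the file, so whether the form itself sets out the visit schedule cannot be checked.

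**Conclusion.** The inconsistency is real and should be corrected. For subjects whose lead is inserted at a clinic visit before the day of surgery, at least those recruited by the alternative route in Section 11, the Section 12 schedule places written consent up to 7 days after an invasive study procedure, against the protocol's own rule. The conclusion assumes only that the Section 11 visit takes place as described. The number of subjects and centers concerned is unknown.

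There is no effect on power, allocation or the primary models, and no bias between arms.

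A reader might also infer that the Table 2 baseline, set before surgery on day 0, is invalid because it could follow insertion and test stimulation. The documents do not support that. Section 9 defines that baseline explicitly, the contrary order is only inferred from the sequence of paragraphs, and either timing precedes randomization. Moving the baseline would also split a day-0 column that serves the day 0–7 end points. No change to the baseline is proposed.

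**What to change.** Amend the two day-of-surgery sentences in Section 12 so that written consent is signed before lead insertion, at the insertion visit or earlier, whichever day that is. The baseline instruments mentioned in the first of those sentences can stay on the day of surgery, as Section 9 has them.

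In Section 9, *Data collection*, replace the reference to the day of enrollment with the day of surgery. The later *Enrollment* paragraph, under *Study Implementation*, already uses that term for the same telephone follow-up.

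Dropping the early visit is not a good alternative, because Section 11 relies on it to justify both waivers.

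The cost is a short wording amendment, sent to the DSMB, each center's IRB and the funder's oversight body, as Section 9 (*Preparation for the UH3 Clinical Trial*) requires for revisions. Someone authorized to take consent must be present at the insertion visit unless the form was signed before it. Sample size, randomization, end points and analyses do not change.

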13. ALTERNATIVES TO STUDY PARTICIPATION

Patients can decline enrollment. If they do so, they will still receive the standard-of-care postoperative analgesia.

14. POTENTIAL RISKS

The procedures and devices used in this study are already 510k cleared by the United States Food and Drug Administration to provide postoperative analgesia. However, there may be risks that are not yet known, and the incidences provided are all estimated with the exception of lead fracture.

Potential risks include infection (<0.01% for up to 60 days of infusion),⁵ lead fracture (7.5%), lead dislodgement (<1%), nerve injury (<0.001%), bleeding (<0.01%), skin irritation (1-5%), lead migration (<0.1%), increased surgical pain, and discomfort/pain on insertion and/or during stimulation (10%).

In addition, there is the risk of loss of confidentiality. The following study procedures will be done to maintain confidentiality of this study: hard copies will be kept in locked medical offices and the locked Investigational Drug Service's files. Any digitized records containing personal health information will be stored as password-protected and encrypted files.

15. RISK MANAGEMENT PROCEDURES AND ADEQUACY OF RESOURCES

The principle protection for participants and the true foundation for conducting a safe and effective clinical study is a well-trained and caring research staff. The principle investigator of this proposal, [name], is an experienced multicenter clinical trial Principal Investigator with a Master's of Science Degree in Clinical Investigation that included multiple classes specifically addressing the ethical conduct of human subjects research. [name] has published special articles within peer-reviewed journals specifically addressing this issue ([name]: Informed consent for medical research: an ethical imperative. *Reg Anesth Pain Med* 2006; 31: 353-7. PMID: 16857555). All study personnel will receive training in human subjects protection and compliance with the HIPAA regulations.

Subjects will be given clear instructions to call an investigator with any questions or concerns regarding their study participation. If a patient experiences an injury that is directly caused by this study, only professional medical care that they receive at the medical center. No other compensation is offered. Any adverse events will be reported to the IRB using the standard adverse events reporting and upon continuing review (depending on severity, as defined by the IRB). During stimulation, subjects will be contacted daily by an investigator, and subjects will have a physicians' pager and cellular phone numbers available to respond 24 hours/day and 7 days/week until the day following lead removal. This procedure has proven effective for ambulatory surgical patients with perineural local anesthetic infusions (continuous peripheral nerve blocks).

Precautions and responses to possible specific adverse events:

Infection: Leads will be placed under sterile conditions as is standard-of-care for any percutaneous device insertion. In addition, all patients having orthopedic surgical procedures receive perioperative antibiotics, which will further decrease any risk of infection. Subjects will be called daily and asked

about signs and symptoms of lead infection. Should a lead become infected, it will be removed and oral antibiotics prescribed.

Lead fracture: It remains unknown what leads to lead fracture in a small percentage of patients, and therefore we cannot take specific steps to minimize its occurrence other than removing the leads with continuous, gentle traction.

Lead dislodgement and migration: Leads include a small “anchor” at the distal end to help keep the lead from withdrawing. In addition, the leads are shaped as a helical coil, which means they “unravel” if pulled on outside of the skin—the tip of the lead is withdrawn only after the entire lead has uncoiled with traction. Therefore, inadvertent dislodgement and migration are extremely unlikely. An occlusive dressing is used to affix the lead to the skin.

Nerve injury: Leads never intentionally come into contact with the nerve—they are inserted 0.5-2.0 cm distant from the target nerve. Therefore, a nerve injury should—theoretically—only occur with accidental contact with the target nerve. The investigators are all specifically trained and have experience inserting perineural catheters using ultrasound guidance, which permits real-time visualization of the insertion needle and target nerve.

Bleeding: Exclusion criteria include ongoing active anticoagulation and/or bleeding disorders to decrease the risk of bleeding. During insertion, vessels are avoided with the use of real-time ultrasound guidance. The investigators are all specifically trained and have experience inserting perineural catheters using ultrasound guidance.

Discomfort: Subjects will have a single-injection peripheral nerve block with long-acting local anesthetic prior to surgery and be provided with a prescription for an oral opioid. Therefore, if the electrical leads provide an inadequate degree of analgesia, subjects will take their oral opioids.

Confidentiality: The risks to confidentiality are the release of names/ telephone numbers/ demographic data (e.g. weight, age, height), which will be minimized by the use of password-protected computers and case report forms that will be stored in locked offices.

The study will have a designated medical monitor, [name], who will remain completely independent of the investigative team and will be a strong subject advocate. The Medical monitor will oversee volunteer recruitment, volunteer enrollment, data collection, data storage, data analysis, and will report any discrepancies or problems to the Institutional Review Boards of both the enrolling center and lead center (University of California San Diego), as well as the Army Human Research Protections Office. The Medical monitor will have the authority to stop the clinical trial at any time, and take any actions necessary to protect the safety and well-being of research volunteers until the Institutional Review Boards can assess the situation(s). In addition, the Medical monitor will review all adverse events and provide a written opinion regarding the relationship and outcome of any unanticipated problems related to participation, serious adverse events, and subject deaths.

The study Data Safety Monitoring Board (DSMB) will be comprised of the Medical Monitor, a physician experienced in both clinical trial management and the ethical conduct of research ([name]), and a statistician, also well-experienced in multicenter trials ([name]). All three of these individuals will be completely independent of the investigative team. No member of the DSMB will have any financial, proprietary, professional, or other interests that may affect

impartial, independent decision-making by the DSMB. The board will comprise individuals with no vested interest in the outcome of the research study. The members will also sign a confidentiality statement. The DSMB will operate from a charter describing its role, membership, reporting procedures, and meeting protocol. The DSMB will decide on its own protocols, set triggers for data review or analyses, and establish guidelines for monitoring the study, stopping the study for safety concerns, and for efficacy based on plans specified in the protocol. Confidentiality will be maintained during all phases of DSMB review and deliberations. DSMB members will maintain strict confidentiality concerning all privileged trial results provided to them. The board will perform the following functions:

- Approval of the trial protocol before enrollment of patients
- Review the data in order to determine efficacy, futility, and safety, and to determine whether the study should continue
- Review data quality and data integrity
- Evaluate risk versus benefit by thorough examination of the data accumulated
- Determine whether the trial is proceeding as planned, the protocol is being followed, the recruitment of patients is on schedule, and data are being collected with the proper accuracy
- Review patient dropouts, if any, and make appropriate recommendations
- Determine whether safety concerns have been raised by the experimental or control treatments

Review Items. Items to be reviewed by the DSMB include:

- Interim/cumulative data for evidence of study-related adverse events
- Interim/cumulative data for evidence of efficacy according to pre-established statistical guidelines in the study protocol
- Data quality, completeness, and timeliness
- Performance of individual centers
- Adequacy of compliance with goals for recruitment and retention, including those related to participation of women and minorities
- Adherence to the protocol
- Factors that might affect the study outcome or compromise the confidentiality of the trial data (such as protocol violations etc.)
- Factors external to the study such as scientific or therapeutic developments that may impact participant safety or the ethics of the study

Recommendations. The DSMB will conclude each review with their recommendations to the principal investigator and primary site Institutional Review Board (at the University of California San Diego) as to whether the study should continue without change, be modified, or terminated. Recommendations regarding modification of the design and conduct of the study may include:

- Modifications of the study protocol based upon the review of the safety data
- Suspension or early termination of the study or of one or more study arms because of serious concerns about patients' safety, inadequate performance, or rate of enrollment
- Suspension or early termination of the study or of one or more study arms because study objectives have been obtained according to pre-established statistical guidelines
- Optional approaches for executive committee and investigators to consider when the DSMB determines that the incidence of the primary study outcomes is substantially less than expected, such as recommendations to increase the number of trial centers or extend the recruitment period
- Corrective actions regarding a study center whose performance appears unsatisfactory or suspicious

Appropriate reports will be made to the Institutional Review Boards at all enrolling centers and the executive committee, comprised of all co-investigators and site directors

Patient Serious Adverse Event Reporting. All unanticipated events and adverse events will be reported to the specific center's Institutional Review Board (IRB), the primary supervising IRB (University of California San Diego), the study Data and Safety Monitoring Board (DSMB), and the Army Human Research Protections Office. The adverse event and unanticipated event profile will be discussed at monthly executive committee video-conference meetings.

Management of adverse events. Adverse events for study-related injuries will be managed by the site director of each center. For a medical emergency that is potentially life-threatening, subjects will be instructed to dial 911 for emergency services to go directly to their location, and the site director will meet the subject at the site's emergency department.

In the event of a study-related injury, the treatment institutions will provide medical care needed to treat those injuries without cost to study subjects. The institutions will not provide any other form of compensation for study-related injuries. This information is specified within the informed consent forms. The forms also instruct subjects to contact the local Institutional Review Board, the enrolling investigator, or the principal investigator of the study for further information (phone numbers provided for all entities). In addition, active duty United States Armed Forces service members who enrolled at a civilian institution who sustain a research-related injury may receive medical care at a military hospital or clinic free of charge. The informed consent form instruct active duty service members to contact the United States Army Medical Research and Materiel Command (USAMRMC) Office of the Staff Judge Advocate (legal office) for issues that are inadequately resolved (with phone number).

